### **10.4 Effectiveness Analyses**

Effectiveness data will be analyzed as observed, as this is an observational registry. The number of patients with non-missing baseline and visit values, baseline mean, visit mean, mean and standard deviation of change from baseline will be provided for continuous variables. Counts and percentages will be provided for categorical variables.

The effectiveness data will be summarized for the All Treated Patient Population (from the first dose in the registry).

The baseline measurements used in the effectiveness tables for this registry are measurements on or before the first day in the registry, except that for the subjects who are rolled over from a prior AbbVie study (Study DE038 and Study M10-444), the baseline measurements will be the baseline measurements collected in the prior study (Study DE038 and Study M10-444).

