## 5.0 Registry Objectives

The primary objective of this registry is to evaluate the long-term safety of Humira in patients with moderately to severely active polyarticular or polyarticular-course JIA who are prescribed and treated in accordance with the approved local Humira product label under the conditions of a routine clinical setting. Patients being prescribed and treated with MTX per the approved local product label will be considered a reference group.

The secondary objective of this registry is to evaluate the long-term effectiveness of Humira in patients with moderately to severely active polyarticular or polyarticular-course JIA who are prescribed and treated in accordance with the approved local Humira product label under the conditions of routine clinical setting. In addition, the impact of treatment interruptions on the safety and effectiveness of Humira will be evaluated as well. Patients being prescribed and treated with MTX per the local product label will be considered a reference group.

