## **6.1 Selection of Population**

Once a decision has been made between the physician and the patient to use Humira (monotherapy or combination therapy with MTX) or MTX (without Humira) as part of usual care for and in accordance with approved local prescribing information for polyarticular JIA, sites will be encouraged to offer enrollment to all eligible patients. After a decision to prescribe Humira, patients from previous Humira clinical trials (Study M10-444 and Study DE038) will be offered enrollment in the registry. Prior to collecting registry-related information, a parent or legal guardian must sign a parental consent and patient assent/authorization form, or appropriate forms per local requirements for release of information. Physicians should determine the appropriate therapy for each patient without regard to study participation. The participating physician will provide the patient a prescription for Humira (monotherapy or combination therapy with MTX) or MTX (without Humira) along with instructions for appropriate use in patients with moderately to severely polyarticular JIA.

Patients prescribed Humira rolling over from another AbbVie clinical study will continue in the Humira arm.

New patients may be enrolled in one of two arms, the Humira arm or the MTX arm, depending on the treatment decision made by the physician prior to enrollment.

Patients in the Humira arm may be treated with Humira alone or in combination with MTX.

Patients in the MTX arm may be treated with MTX alone or in combination with other DMARDs, but not with anti-TNFs or other biologic therapies.

Patients who are non-responders, intolerant to MTX treatment arm or are in need of combination treatment with Humira therapy are eligible to switch to the Humira treatment arm up until enrollment of the last patient into the registry (i.e., until enrollment in the Humira treatment arm is complete).

In these cases patients will be required to discontinue from the MTX arm and consent as a new patient in the Humira arm once any Adverse Events of Special Interest and SAEs have been resolved or the AbbVie Study Designated Physician should be contacted to assess the eligibility of a patient to enroll in the Humira treatment arm if an AE is ongoing and eligibility criteria are met.

The 10-year follow-up time for these patients begins when these patients start the Humira arm and not the date they started the registry within the MTX arm.

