After the registry enrollment period is closed to the Humira arm, patients wishing to switch to Humira will be discontinued from the MTX treatment arm; however, the patient will be encouraged to remain in the registry and efforts will be made to follow these patients through Year 10 to gather safety data.

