**With Humira, eow or Methotrexate (as directed)**

eow = every other week

\* For patients not rolling over from Study DE038 or Study M10-444.

\*\* Participation in the registry may be longer if patient switches from MTX arm to HUMIRA arm.

\*\*\* The Direct to HCP Follow-up Process will collect events annually.

The physician will then follow the patient during regular office visits at intervals as information about medications taken for polyarticular JIA will be recorded on the CRF at enrollment and at visits closest to the time points in [Table 1](#). While the physician may deem it appropriate and necessary to have the patient return for additional visits during the observation period, data will be collected via Case Report Forms (CRFs) only at the intervals that most closely correspond to those described in [Table 1](#). However, information related to safety should be captured at any time using the appropriate eCRFs.

Physicians should treat their patients as they would in their routine clinical practice. At any time, patients and physicians may choose to interrupt Humira (monotherapy or combination therapy with MTX) or MTX (monotherapy without Humira) therapy for any reason. Patients that intermittently stop treatment ([Section 10.1](#)) should continue to be monitored during and after their treatment interruption for safety (SAEs and AEs of Special Interest) and effectiveness. These patients will be asked for changes in their polyarticular JIA medications, concomitant medication and medical history at their baseline visit and at their regularly scheduled visits..

Patients that switch from the MTX arm to the Humira arm will be followed as patients in the Humira arm.

If treatment with Humira (monotherapy or combination therapy with MTX) and/or MTX (without Humira) is permanently discontinued for any reason, patients will be encouraged to remain in the registry. The reason for discontinuation should be documented on the eCRF.

Office visits are optional for patients that discontinue treatment, if the patient is not seen at a visit; both active and passive methods will be used to maintain contact. During enrollment, the patient will be asked by the investigator to provide contact information in accordance with local regulations. All patients who are unreachable after 3 consecutive documented attempts to contact the patient via phone, email, or certified letter, will be considered lost to follow-up.

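### MTX patients who switch to Humira leave the MTX denominator at later visits, so the as-observed MTX reference response rate is biased upward if non-responders switch more often than responders

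*Supplement*

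**What the plan says.** Section 5.0 gives the MTX arm its role in the secondary, effectiveness objective: "Patients being prescribed and treated with MTX per the local product label will be considered a reference group".

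Section 6.1 defines the route out of that arm: "Patients who are non-responders, intolerant to MTX treatment arm or are in need of combination treatment with Humira therapy are eligible to switch". The route is open until Humira enrolment is complete. On taking it, "patients will be required to discontinue from the MTX arm and consent as a new patient in the Humira arm". Section 6.6 adds: "Patients that switch from the MTX arm to the Humira arm will be followed as patients in the Humira arm".

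Once Humira enrolment has closed, section 6.1 reads differently: "patients wishing to switch to Humira will be discontinued from the MTX treatment arm; however, the patient will be encouraged to remain in the registry". That paragraph speaks only of gathering safety data. Section 6.6.4 treats Humira started at that stage as a concomitant medication.

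Section 10.4 sets the analysis: "Effectiveness data will be analyzed as observed, as this is an observational registry". For continuous variables, "The number of patients with non-missing baseline and visit values, baseline mean, visit mean, mean and standard deviation of change from baseline will be provided". It promises counts and percentages for categorical variables. Section 10.4.1.2 summarises PedACR30/50/70/90 descriptively at each registry time point. The population is All Treated (section 10.1).

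**The concern.** A patient for whom MTX fails and who moves to Humira is counted as an MTX non-responder up to the switch and is absent from the MTX table afterwards. The missing value is then related to the outcome being summarised. Someone who switches soon after Month 6 is missing from up to nine later MTX visits (Months 12 to 60 in Table 1).

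The MTX arm is there so that Humira's long-term effectiveness can be read against something. If its later visits increasingly hold the patients who did well enough to stay on MTX, the reference for PedACR and inactive disease looks better than MTX performed in the patients who started it. Means of JADAS and the core-set variables are subject to the same selection.

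**Working it through.** **No plan figure to reproduce.** The protocol gives no MTX response rate, no switch rate and no power for effectiveness. Its one power statement (section 10.6, about 97% for serious infections in the Humira arm) is not affected by this point.

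**Does any rule keep switchers as MTX failures?**

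- Section 10.4 has no non-responder rule.
- The only carry-forward rule, in section 10.4.2, concerns Humira treatment interruptions.
- Section 10.2 cuts MTX exposure at the first Humira dose, but no matching rule is given for MTX effectiveness data.

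So a switcher leaves numerator and denominator together.

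**Formula.** At a visit after the switches, let

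- p = response rate if every MTX starter were kept in the arm's denominator,
- s = share of all MTX starters who have switched,
- r = share of switchers who were MTX responders.

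As-observed rate = (p − r·s)/(1 − s). Overstatement = s·(p − r)/(1 − s).

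The overstatement is positive when r < p, that is, when non-responders switch more often than responders. It is zero when r = p.

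**Numbers.** All of p, s and r are assumptions.

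| s | p = 60%, r = 0 | p = 60%, r = 1/3 | p = 50%, r = 0 |
|---|---|---|---|
| 10% | 0.600/0.90 = 66.7% (+7) | 0.567/0.90 = 63.0% (+3) | 0.500/0.90 = 55.6% (+6) |
| 20% | 0.600/0.80 = 75.0% (+15) | 0.533/0.80 = 66.7% (+7) | 0.500/0.80 = 62.5% (+12.5) |
| 30% | 0.600/0.70 = 85.7% (+26) | 0.500/0.70 = 71.4% (+11) | 0.500/0.70 = 71.4% (+21) |

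The r = 0 columns are upper limits for their p and s. With p = 60% and s = 30%, r = 0 means that 30 of every 40 non-responders have switched, which is extreme.

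**In patients.** Take the planned 300 MTX patients, p = 60% and s = 20%: 180 responders, 120 non-responders, 60 switchers.

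- All 60 are non-responders: 180/240 = 75.0%.
- 20 of the 60 are responders: 160/240 = 66.7%.
- Everyone kept and classified by MTX response: 180/300 = 60.0%.
- All 60 switchers counted as failures, 20 of them responders: 160/300 = 53.3%.

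The last line shows that counting every switch as failure can fall below p. Such a table therefore belongs beside the as-observed one and should not replace it.

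**The two arms side by side.** No provision moves a failing Humira patient into the MTX arm. In either arm, patients who stop treatment without changing arm are encouraged to stay, with effectiveness followed through Year 5 (sections 6.7.2 and 6.8.1). Their visits become optional, however (section 6.6), and effectiveness is not collected in the direct-to-HCP process (sections 6.5 and 7.3).

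**The case against.** The strongest case against the point has five parts.

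1. **Not every MTX failure is removed.** This stands. Switching is optional, visits before the switch count, and MTX patients who stop without switching may stay and be assessed. A reader might infer that the MTX tables come to describe only patients for whom MTX worked. The text does not support that, and even the upper-limit figures leave 14% to 33% non-responders in the table at p = 60%.

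2. **The window is limited.** This stands. The transfer ends when Humira enrolment is complete, and recruitment was planned over three years (section 10.6), so late enrollees have little time to switch. After closure the handling is simply unclear. If effectiveness data from those patients stop, the same selection continues. If their values on Humira count under MTX, response to Humira can raise the MTX rate.

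3. **The Humira arm also loses failures.** This stands. Lack of effectiveness and use of another biologic are listed reasons for stopping treatment (section 6.8.1), and the sample size allows for about 68% dropout in the Humira arm. A reader might infer that the loss is wholly one-sided, or that the Humira-MTX gap could vanish or reverse. Neither is shown. What is particular to MTX is a formal transfer out of the arm on failure.

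4. **Non-response is one of three switch reasons.** This stands, and it is why the r = 1/3 column is given. The bias disappears only if responders switch as readily as non-responders, which is unlikely when non-response is a named ground.

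5. **The analysis is descriptive and a SAP could add rules.** No formal test is affected, and patient numbers by visit will show the MTX denominator shrinking. No SAP is shown. But the protocol itself fixes the as-observed choice, and a shrinking denominator does not tell the reader why patients left.

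**Conclusion.** The concern holds in direction. For switches made while Humira enrolment is open, the as-observed MTX response rate at later visits is biased upward to the extent that non-responders switch more often than responders.

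The size cannot be computed from the documents. At an assumed 60% response among all starters with 10% to 30% switched, it is at most 7 to 26 points, and about 3 to 11 points if one third of switchers are responders. Because attrition may enrich the Humira arm as well, the net effect on the gap between arms is unknown. What suffers is interpretation of the secondary objective. The change should be made, but nothing in the plan fails without it.

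**What to change.** Keep the as-observed tables. Add to section 10.4 a supplementary table for PedACR30/50/70/90 and inactive disease on the All Treated Population, with this rule:

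- A patient in either arm counts as a non-responder in that arm at every later scheduled visit through Year 5 if the patient permanently stops the arm's treatment for lack of effectiveness or intolerance, or starts Humira (MTX arm) or another biologic.
- The rule applies whether or not the patient stays in the registry.

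Show the number of such patients and their reasons by arm and visit. Read the Humira results against the MTX reference using both tables.

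The trigger must be the treatment event. If it were departure from the arm, it would fall mainly on MTX patients, because Humira patients who stop for inefficacy can remain in their arm. The rule also settles how responder status is counted for MTX patients who start Humira after enrolment closes.

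**Cost:** a short paragraph and one extra table per responder endpoint. Treatment stop dates, reasons for stopping and JIA medications are already collected (sections 6.6.4, 6.6.11 and 6.7.2), and neither data collection nor patient care changes.

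**Limits:** some patients counted as failures might have responded later, and some who stop for intolerance were responders. Patients lost for other reasons are still handled as observed. JADAS and the core-set means are not corrected, so they should be read with the counts by visit.

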### **6.7.2 Safety Variables**

The physician will be asked to document SAEs and Adverse Events of Special Interest (AESI) on eCRFs (Section 7.0).

SAEs and Adverse Events of Special Interest (AESI) will be reported to AbbVie from the time the physician obtains the patient's authorization to use and disclose information (or the patient's informed consent/patient authorization) throughout the registry or Direct to HCP follow-up process until satisfactory conclusion or until 70 days following last dose of registry drug (whichever is longer). In the event Humira therapy is interrupted, SAEs and Adverse Events of Special Interest (AESI) will be collected throughout the interruption. If a patient switches from MTX to Humira treatment, SAEs and AEs of Special Interest will continue to be collected under the Humira arm. If treatment with Humira or MTX is permanently discontinued for any reason, patients will be discontinued from treatment and the reason for discontinuation will be recorded on the Study Drug Completion eCRF. Patients that discontinue treatment will be encouraged to remain in the registry and will be followed for safety and effectiveness through Year 5 and SAEs and AESI will be followed until satisfactory conclusion or until 70 days following last dose of registry drug (whichever is longer), and starting at Year 6, patients will be followed annually for the subset of AESI which include congestive heart failure and malignancies and SAEs through Year 10 of the registry until satisfactory conclusion or until 70 days following last dose of registry drug (whichever is longer). For polyarticular

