## **6.8 Removal of Patients from Therapy or Assessment**

### **6.8.1 Discontinuation of Individual Patients**

A patient may withdraw from the registry at any time without prejudice due to withdrawal of consent, lost to follow-up as defined below, or death.

If the Physician, for any reason, decides it is in the best interest of the patient to discontinue Humira or MTX, treatment should be stopped. A patient that discontinues Humira or MTX treatment will be encouraged to remain in the registry. Efforts will be made to follow all patients through Year 5 of the registry for safety and effectiveness and from Year 6 through Year 10 congestive heart failure, malignancies, pregnancies and SAEs. For polyarticular JIA patients 2 to < 4 years of age in countries with available local approval for this group of patients at the time of consent to the registry the AESI,

SAEs and pregnancy (potentially during the study at the age when patient can become pregnant) will be collected for the full 10 years as defined by the protocol (Figure 2). The following reasons, but not limited to, for treatment discontinuation should be noted on the eCRFs.

Clinically significant abnormal laboratory results or AEs, which prevent continuation of Humira (monotherapy or combination therapy with MTX) and/or MTX (monotherapy without Humira) as determined by the Physician.

The physician believes it is in the best interest of the patient.

The parent, legal guardian, or patient requests withdrawal from the registry.

The patient is lost to follow-up, i.e., does not provide data for 1 year and does not respond to notifications from the site.

The patient receives a concomitant biologic anti-rheumatic therapy other than Humira.

The patient is diagnosed with a malignancy except for localized non-melanoma skin cancer. Discontinuation for carcinoma-in-situ is at the discretion of the Physician.

Patients who interrupt their Humira or MTX therapy and do not restart within 1 year.

Lack of effectiveness.

Patients who have discontinued from the registry prior to Year 10 will be contacted to determine interest in participation in direct to HCP process that includes the HCP's completion of a simplified HCP questionnaire on an annual basis.

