### **10.1 Analyzable Populations**

The All Treated Population is defined as patients who receive at least one dose of MTX or Humira in the registry. The All Treated Population will be used for analysis of safety and effectiveness.

In addition, the Intermittent Treatment Population, defined as Humira patients who have at least one treatment interruption in Humira dosing, will be used in the analysis of safety and effectiveness.

A treatment interruption (TI) for a patient will be defined as a period of > 70 consecutive days during which a patient does not receive any Humira injections. The first day of the TI will begin 71 days after the previous injection of Humira. For patients who receive another Humira injection after the TI, the last day of the TI will be defined as the day before the patient receives the next injection (i.e., the first post-TI Humira injection; see Figure 3). Note that a patient may have multiple TIs. If a patient fails to restart Humira within 1 year of the last Humira injection, then that patient will not be included in the Intermittent Treatment Population.

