## **10.6 Determination of Sample Size**

The proposed sample size for this registry is approximately 800 patients. Due to the low incidence and prevalence of the disease, the size of the registry has been chosen based on the expected availability of eligible patients to be enrolled in a three year time frame. The estimated recruitment rates were based on published articles and advice from one leading pediatric rheumatology site.

It is planned that a total of 800 patients will be enrolled to this registry in a ratio of 5:3 corresponding to the Humira arm or the MTX arm respectively. The sample size determination is based on the rate of serious infectious AEs in the Humira arm. Assuming a total of 500 patients with full 5 years of follow up in the Humira arm, a maximum total exposure to the Humira in this registry can be 2500 patient years. Typically a higher rate of dropout is expected in a registry compared to traditional controlled studies. Allowing for approximately 68% dropout, a total of approximately 1500 patient years exposure in the Humira arm will have approximately 97% power, using a two-sided test at level of significance  $\alpha = 0.05$ , to detect a rate of serious infectious AE of 4.8 events per 100 patient years from the rate of 2.8 events per 100 patient years previously seen in this population in Study DE038.

Due to low frequencies of malignancies and congestive heart failure (CHF), patients will be followed for an additional 5 years.

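### By-visit effectiveness is summarized without regard to current drug, so late-visit results cannot be attributed to Humira or MTX and could err in either direction

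*Supplement*

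**What the plan says.** Section 5.0 sets the target: "The secondary objective of this registry is to evaluate the long-term effectiveness of Humira", with MTX patients as a reference group. Section 10.4 gives the method, "Effectiveness data will be analyzed as observed, as this is an observational registry", and the set: "The effectiveness data will be summarized for the All Treated Patient Population (from the first dose in the registry" onward. Section 10.1 defines that set by a single dose: "The All Treated Population is defined as patients who receive at least one dose of MTX or Humira in the registry".

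Data continue after drug stops. Section 6.7.2 says: "Patients that discontinue treatment will be encouraged to remain in the registry and will be followed for safety and effectiveness through Year 5". Section 6.7.1 adds that effectiveness is also collected during a Humira interruption. Attendance after stopping is voluntary (Section 6.6): "Office visits are optional for patients that discontinue treatment". Section 6.5 says that the direct to HCP process collects no effectiveness measures.

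The reasons for stopping treatment in Section 6.8.1 include lack of effectiveness and this one: "The patient receives a concomitant biologic anti-rheumatic therapy other than Humira". The same section encourages patients who stop treatment to stay in the registry.

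**The concern.** The tables meant to serve the secondary objective have a start but no end tied to drug. A Month 60 value in the Humira column may come from a patient on Humira, in an interruption, off all biologics, or on a different biologic. Patients who leave the registry are absent from that column, and patients who stopped drug but stayed appear only if they choose to attend.

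Two reasonable questions are how patients do while on Humira, and what share of starters are still benefiting. The late-visit figure answers neither. The same applies to the MTX reference column, which weakens any descriptive comparison between the arms.

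**Working it through.** **1. Effectiveness beside safety in the same protocol**

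| Feature | Effectiveness (10.4) | Safety (10.2, 10.3) |
|---|---|---|
| Start | First registry dose | First day in registry, first registry dose or first recorded dose, by summary |
| End tied to drug | None stated | Treatment-emergent summaries end 70 days after last dose |
| Interruptions | Not excluded | Excluded from treatment-emergent summaries |
| MTX patient who starts Humira | No cut stated | MTX exposure ends at first Humira dose |
| Summary regardless of drug | Yes, the only by-visit one | Yes, the observational summary, beside the treatment-emergent ones |

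The plan links outcome to drug for safety but not for effectiveness. The one effectiveness analysis tied to drug status is the interruption analysis in Section 10.4.2, which asks only whether response recovers after a Humira interruption.

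**2. The plan's own attrition figure**

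Section 10.6 gives 500 Humira patients, 5 years and a maximum of 2500 patient-years, then: "Allowing for approximately 68% dropout, a total of approximately 1500 patient years exposure".

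- Constant hazard: λ = −ln(1 − 0.68)/5 = 0.2279 per year. Patient-years = 500 × 0.68/0.2279 = 1492, against about 1500 stated, so this reproduces.
- Uniform dropout would give 500 × (0.32 × 5 + 0.68 × 2.5) = 1650. Simply taking 2500 × 0.32 gives 800.
- The stated power of about 97% (safety, 4.8 against 2.8 events per 100 patient-years, so 72 against 42 expected events) also reproduces: 97.8% by exact Poisson test. No planning figure is given for effectiveness.

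Because Section 10.6 speaks of exposure, I read the 68% as leaving Humira. The numbers still on drug at Years 1 to 5 are then 398, 317, 252, 201 and 160 of 500, leaving 340 stoppers by Year 5. The protocol does not say whether the 68% means leaving drug or leaving the registry.

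**3. How far the Year 5 figure can move**

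The protocol gives no response rates, so the following are assumptions: 80% of the 160 persisters respond (128 patients), a share f of the 340 stoppers is assessed, and a share r of those assessed responds.

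As observed = (128 + 340·f·r)/(160 + 340·f)

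| Stoppers assessed | r = 20% | r = 95% |
|---|---|---|
| None | 128/160 = 80.0% | 80.0% |
| 25% (85) | 145/245 = 59.2% | 208.75/245 = 85.2% |
| All (340) | 196/500 = 39.2% | 451/500 = 90.2% |

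- Against on-drug response (80%): from 39.2 − 80 = −40.8 points to 90.2 − 80 = +10.2 points.
- Against a strict rule with every stopper a non-responder (128/500 = 25.6%): from 39.2 − 25.6 = +13.6 points to 90.2 − 25.6 = +64.6 points.

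With 90% response in persisters (144 patients), the on-drug comparison runs from 212/500 − 90% = −47.6 points to 467/500 − 90% = +3.4 points.

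**4. Direction when some attendees are on another biologic**

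Suppose the table shows 75% and 20% of attendees are on another biologic (both assumed).

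- If 60% of the switched patients respond, they contribute 0.20 × 0.60 = 12 points. On-drug response is (0.75 − 0.12)/0.80 = 78.75%, so the table is too low.
- If 90% respond, they contribute 18 points. On-drug response is (0.75 − 0.18)/0.80 = 71.25%, so the table is too high.

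The sign depends on how switched patients fare relative to persisters, which the protocol cannot tell us.

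**The case against.** The strongest reply is that following all treated patients regardless of later drug is a recognised choice for a registry, and that effectiveness here is secondary, descriptive and untested. Sections 10.4 and 10.4.1 already show the number of patients with data at each visit, and Section 10.2 tabulates registry discontinuations by reason. No SAP is among the documents, and on-drug cut-offs or missing-data sensitivity analyses are often left to one.

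Part of this stands. The as-observed table is legitimate and should stay, and the absence of sensitivity analyses from a protocol would not by itself be a fault. But the point concerns a population and method that Section 10.4 states. Counts of patients with data do not show what drug those patients are taking.

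Three stronger readings are tempting and are not supported:

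- *The tables overstate Humira's effectiveness.* Loss of non-responders and good response on another biologic push the figure up. Stoppers who flare and still attend push it down. Steps 3 and 4 show both signs.
- *MTX failures later treated with Humira count as MTX responders.* While Humira enrollment is open, Section 6.1 moves switchers to the Humira arm under new consent. After it closes, Section 6.1 discontinues them from the MTX arm and follows them for safety. Section 6.6.4 excludes patients needing a biologic from the MTX arm, yet lets them continue in the registry and treats later Humira as a concomitant medication. What remains is an unclear rule, not a demonstrated misattribution.
- *True Year 5 response is only about a quarter of starters.* The 25.6% counts every stopper as a non-responder, including any who stopped because they were well. It is a lower bound under the assumptions above.

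The other-biologic route is also uncertain. Section 6.6.4 says other biologics are not to be given concurrently during participation, while Section 6.8.1 anticipates them. Use after Humira has stopped remains possible, but the number of such patients is unknown.

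**Conclusion.** The point holds as one of attribution, not of a known bias. The stated effectiveness summaries combine on-drug, off-drug and switched patients in a self-selected set, so late-visit results cannot be attributed to Humira or MTX.

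Under the assumptions in step 3, the Year 5 figure could lie about 41 points below to 10 points above response while on Humira. It would lie about 14 to 65 points above the strict non-responder count. That second gap shrinks as more patients stop for reasons other than treatment failure. These are ranges over assumed inputs, not predictions, and they rest on reading the 68% as leaving drug.

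The primary safety objective is unaffected. The change is worth making because the secondary objective depends on these tables and the remedy is cheap.

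**What to change.** 1. Keep the as-observed table in Section 10.4, labelled as regardless of current treatment.
2. Add an on-drug by-visit summary using the plan's own safety window: from first registry dose through 70 days after last dose, excluding interruptions, and ending at the start of another biologic or, in the MTX arm, at the first Humira dose. Show off-drug visits separately.
3. At each visit, give counts by current treatment: the arm's drug, interrupted, off drug, another biologic, not assessed.
4. Add one sensitivity table with a fixed denominator. Patients who stopped for lack of effectiveness or intolerance, or moved to another biologic, count as non-responders from that point. State a rule for patients lost for other reasons, including those who stopped because they were well.
5. Reconcile Sections 6.1, 6.6.4 and 6.8.1 on whether patients who receive another biologic, or Humira after MTX, contribute effectiveness data, and to which arm.

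The cost is analysis wording and one or two extra tables. Dosing dates, reasons for stopping and concomitant JIA therapies are already collected (Table 1 and Sections 6.6.4, 6.6.11 and 6.8.1), so no new data are needed. The downside is small: late response figures may change, in either direction.
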